6.4 Study Overview

To confirm or reject the hypotheses a prospective, double-blind, randomized controlled trial (RCT) is designed to investigate the clinical performance of resin-infiltration as early caries management in a caries-prone population.

This CIP describes a three-year longitudinal, prospective, randomized controlled trial in split mouth design. The study includes a clinical team involving one on-site Principal Investigator (Site-PI)/operator and one back-up Clinical Investigator (CI)/operator.

The clinical site will enroll 150 subjects (in the age range of 14 years or older) with 2 study lesions. If the lesion management provided in the study appears to be insufficient within the investigated period, the study will provide a maximum of 2 traditional restorations for free to participants. The patients will be evaluated at six time points over a period of 3 years. Lesion status and caries risk will be monitored at 6-month intervals, while radiographic evaluation will be conducted at 12-month intervals at 1-, 2- and 3-year recall visits.

7 Design of the Clinical Investigation

The study will be designed as a controlled, double blind, randomized, prospective trial with a three year follow-up period regarding to CONSORT²² recommendations as a single-center study to investigate the effect of caries infiltration as an alternative treatment option.

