9.3 Randomization

A random assignment of the treatment to teeth is based on equal distribution of the two treatments; each subject will receive both a placebo controlled or an Icon resin treatment for the two proximal carious teeth, assigned by beginning with the tooth with the lowest number, the specific procedure applied to each tooth will be determined by selecting from a box containing two choices (A or B) by the clinician doing the procedure. One tooth (the one with the lowest tooth number in the universal numbering system) will receive the treatment drawn from a box containing the names placebo or Icon. The universal numbering system begins with #1 - the maxillary right third molar and proceeds to #16 the maxillary left molar. In this system the mandibular left third molar is # 17 and the mandibular right third molar is tooth number #32. The treatment (the first one drawn) will be placed on the tooth with the lowest number. The remaining tooth will receive the second treatment. Clinicians and patients

receiving the two treatments will be blinded as to the treatment applied to the specific tooth.

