11.1 Prospective Design

Controlled, randomized, double blind study, single center design.

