11.4.2 Blinding

Both the placebo and the Icon materials are same in their delivery system, material color, and viscosity. Therefore, the investigators are blinded as to the material used, as are the patient and the evaluators.

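### Section 9.3 describes the treating clinician's allocation draw both by code and by treatment name; a named slip would unblind the operator to both study teeth

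*Combined protocol and SAP*

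**What the plan says.** Protocol section 9.3 (Randomization) sets out a within-patient draw for the two study teeth. One sentence has the procedure for each tooth determined by "selecting from a box containing two choices (A or B) by the clinician doing the procedure". The next says that the tooth with the lower universal number "will receive the treatment drawn from a box containing the names placebo or Icon". Then: "The remaining tooth will receive the second treatment". The section closes by saying that clinicians and patients "receiving the two treatments will be blinded as to the treatment applied to the specific tooth".

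Sections 9.4.1 and 9.4.2 both repeat that the treating clinician makes the draw from a box. Neither says what is written on the slips. Section 9.4.2 adds that the sponsor supplies placebo syringes identical to the Icon ones.

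The blinding claim is made in several places. Section 6.4 says that "a prospective, double-blind, randomized controlled trial (RCT) is designed"; section 11.1 reads "Controlled, randomized, double blind study, single center design". Section 11.4.2 gives the ground for it: "Both the placebo and the Icon materials are same in their delivery system, material color, and viscosity". It concludes: "Therefore, the investigators are blinded as to the material used, as are the patient and the evaluators". Section 18.2 refers to a name-code list that can be consulted if unblinding is needed after a serious adverse event.

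**The concern.** Three statements cannot all hold: the treating clinician draws the slip, the slip names the treatment, and the treating clinician is blinded. Site staff who follow the named-slip sentence literally would unblind themselves before touching the first tooth.

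The protocol rests operator blinding on the materials looking and handling alike. That protects an operator who has not been told the allocation. It does nothing for one who has just read the treatment name.

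The design is split-mouth, so the two teeth of one patient are the comparison. An operator who knows one tooth knows the pair. If that operator later scores the same patient, the assessor knows which side of the comparison is which.

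**Working it through.** The point involves no stated figure, so the check sets the passages side by side.

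1. **Who draws.** Section 9.3 names the clinician doing the procedure, in the sentence about A and B. The sentence about names does not itself say who draws, but it concerns the same tooth and the same allocation, and 9.4.1 and 9.4.2 give the draw to the treating clinician. There is one draw, described twice.

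2. **What one slip reveals.** There are two teeth and two treatments. The slip drawn first goes to the lower-numbered tooth and the remaining treatment goes to the other. With a name on the slip, the operator knows 2 of 2 teeth. With an opaque code whose key the operator does not hold, the operator knows 0 of 2.

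3. **Whether the syringes help.** Identical delivery, colour and viscosity (9.4.2, 11.4.2) prevent the operator from inferring the treatment from the product. They cannot remove knowledge gained from the slip.

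4. **Which description fits the rest.** A name-code list (18.2) and matched syringes serve a purpose only if the operator works from codes. The statements in 6.4, 9.3, 11.1 and 11.4.2 that clinicians or investigators are blinded, or that the trial is double-blind, also require codes. The named-slip phrase is the one that does not fit. No visible section says outright that the slips carry codes only, or who holds the list.

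5. **Whether the knowledge can reach outcomes.** It can do so only where someone who treated a patient also scores that patient. Two routes are left open by the visible text:
   - Section 6.4 makes the site principal investigator an operator, and 11.4.3 makes the principal investigator the visual reader of the radiographs. Section 11.4.3 says that the reader is blinded. It is also marked as revised by Amendment 1, whose content is not shown.
   - Section 11.3 has operators who both evaluate teeth and seal lesions, and separately gives recall evaluation to two calibrated examiners. The SAP gives all evaluations to two such examiners. Neither says whether those examiners may also be operators. Their dental examination underlies the SAP's primary outcome, the proportion of lesions needing a filling, and section 9.5 settles disagreements between assessors by consensus.

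6. **What limits those routes.** Under 11.4.3, subtraction images are coded, put in random order and read by an external examiner. An operator's knowledge from the slip has no evident path to that reading, and subtraction is the only endpoint that protocol section 11.4.1 tests formally. Table 14.2 ties lesion-level treatment to stated triggers, which narrows the room for an operator's knowledge to affect the filling outcome, although judgement remains.

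**The case against.** The strongest reply is that this is loose drafting. The two sentences are adjacent, and A and B may simply stand for placebo and Icon. The name-code list, the identical syringes and the repeated blinding statements all support that reading. This stands as the likely intention. It does not remove the conflict, because the reader has to infer it and the text as written instructs something else.

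A second reply is that outcome assessment is separated from treatment: two calibrated examiners at recall, a visual reader said to be blinded, and an external reader for the subtraction images. Much of this stands. It closes the route for any patient scored only by people who did not treat that patient. It does not close it entirely, because no visible sentence keeps an operator from also being an examiner, and the principal investigator appears in both roles.

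A third reply is that the answer may lie in material not visible here, such as the amendments or appendix forms. That cannot be excluded. Sections 8.1 and 11.4.3 carry a note that Amendment 1 revised them; 9.3 carries none.

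A reader might go further and infer that the operators were in fact unblinded and the trial was not double-blind. The documents do not support this: they contain a contradiction, not a record of what was drawn. Nor do they support an inference that the outcomes are biased, since the external subtraction reading is insulated and the overlap of roles elsewhere is only possible. A reader might also try to size the exposure by dividing the 150 patients equally among the operators. No split is given, and section 6.4 calls one of its two operators a back-up, which speaks against equal shares.

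**Conclusion.** The point holds as an internal contradiction with a conditional consequence. As written, section 9.3 contains a procedure that is incompatible with the blinding it states. If named slips are drawn, the operator knows both teeth of that patient and the identical syringes cannot restore the blind. If opaque codes are drawn, the stated blinding can stand.

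The size of any bias cannot be estimated from the documents. It is confined to scores given by someone who treated the same patient, and the number of such patients is not stated; it may be none. The most exposed readings are the visual radiograph score, if the principal investigator treated the patient, and the recall examination behind the filling outcome, if an examiner is also an operator.

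The conclusion assumes that 9.3 is the operative text, unchanged by the amendments that are not shown. Section 6.4 names two operators and section 11.3 names four. That is a separate discrepancy, to be handled on its own, and nothing here depends on it.

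**What to change.** - **Section 9.3:** delete the reference to treatment names in the box. State one draw, using opaque codes matched to coded syringes.
- **Sections 9.4.1 and 9.4.2:** align the sentences on the clinician's draw with 9.3.
- **Section 18.2 or 9.3:** state that the existing name-code list is held by someone who neither treats nor evaluates.
- **Section 11.3:** state that recall examiners and the visual reader do not score patients they treated, as far as existing staff allow.

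The cost is a wording amendment, coded labels on syringes that the sponsor already supplies, one designated list-holder, and a rule for assigning assessors to patients. No visit or patient procedure is added.

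If treatment is already complete, rewording cannot change the draws. In that case, document which form of draw was used and whether any assessor scored a patient he or she had treated. If names were drawn, qualify the double-blind description in the report.

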9.4 Intervention Visit

9.4.1 Intervention Site “TREATMENT”

During the screening examination and after informed consent has been obtained from the subject, bite wing radiographs will be made using a customized holder for the digital sensor using VPS impression material. The subject position will be controlled in 3 dimensions by placing holders in the subject's ears and placing their chin in a holder. The positions used for the initial set of radiographs will be recorded and used for all subsequent x rays to standardize their position at each recall. At a separate appointment, each selected subject will be instructed in oral hygiene procedures to include brushing, flossing and the use of a fluoride containing toothpaste. To be included in this study the subject must have two teeth with similar sized lesions. After the lesions are selected, one of two treatments will be selected from a box by the clinician doing the procedure. One of the “treatment tooth” will randomly receive the infiltrating resin (Icon). Teeth will be isolated with a rubber dam, the tooth surface cleaned with non-fluoride prophylactic paste and pumice. The Icon material will be applied following the manufacturer's instructions and light cured with S 10 curing light (3M ESPE, St Paul, MN). Output from the curing light will be measured and recorded weekly. The Icon infiltrating resin will be polished using interproximal finishing/polishing strips (Sof Lex, 3M ESPE, St Paul, MN). Subjects will be given a letter to take to their local dentist asking them not to treat the selected lesions without informing the investigator first. Subjects will be recalled at 6, 12, 24 and 36 month intervals and at radiographs will be made of the control and test lesions after 12, 24 and 36 month . During all visits, oral hygiene will be reinforced.

9.4.2 Intervention Site “CONTROL”

During the screening examination and after informed consent has been obtained from the subject, bite wing radiographs will be made using a customized holder for the digital sensor using VPS impression material. The subject position will be controlled in 3 dimensions by placing holders in the subject's ears and placing their chin in a holder. The positions on the initial set of radiographs will be recorded and used for all subsequent x rays to standardize their position at each recall. At a separate appointment, each selected subject will be instructed in oral hygiene procedures to include brushing,

flossing and the use of a fluoride containing toothpaste. To be included in this study the subject must have two teeth with similar sized lesions. After the lesions are selected, one of two treatments will be selected from a box by the clinician doing the procedure. One tooth will randomly receive the infiltrating resin (Icon) while the other will receive a placebo. Teeth will be isolated with a rubber dam, the tooth surface cleaned with non-fluoride prophylactic paste and pumice. Syringes identical to the Icon materials will be supplied by DMG for the placebo procedure. The syringes will be filled with the solutions having the same consistency and color as the Icon material. The placebo material will be applied following the manufacturer's instructions and light cured with an S 10 curing light (3M ESPE, St Paul, MN). Output from the curing light will be measured and recorded weekly. The placebo material and the Icon infiltrating resin will be polished using interproximal finishing/polishing strips (Sof Lex, 3M ESPE, St Paul, MN). Subjects will be given a letter to take to their local dentist asking them not to treat the selected lesions without informing the investigator first. Subjects will be recalled at 6, 12, 24 and 36 month intervals and at each recall radiographs will be made of the control and test lesions. During these visits, oral hygiene will be reinforced.

9.5 Follow-up Evaluations

At each recall (baseline, 6-month, one, two and three years) all lesions will be assessed according to the asked criteria. In addition to the clinical and radiographic assessment (see below), each evaluation will include an evaluation of surface roughness, color match, post-operative sensitivity/discomfort, and presence or absence of secondary caries. Every attempt will be made to schedule the six month, one and two year recalls within ± 2 weeks of the recall interval. When assessors differ, a consensus will be reached before the patient is dismissed. In the event an Icon resin is unsatisfactory, details of the mode of failure will be documented and the necessary replacement / repair made.

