14.2 Withdrawal / Dropout of Subjects

Table 14.2 Withdrawal and drop-out of subjects separated by level, reason consequences

Level	Cause	Consequence
Lesion	An allocated lesion progresses radiographically into the middle or inner 1/3 of dentin (scores 4 and 5).	The lesion is treated invasively by removing the caries and placing a filling. The case is scored as "progressed" and "failure".
	The patient shows signs of reversible or irreversible pulpitis in an allocated tooth.	The tooth is treated. The case is scored as "progressed" and "failure".
Patient	The patient shows adverse reactions for one of the study materials.	Counteractive measures are taken. Unwanted effects are documented in CRF and CEF. The patient is scored as "drop out".
	The patient cannot be examined (i.e. x-ray during pregnancy)	The patient is scored as "drop out".
	One or more allocated lesions have been treated by an external dentist.	The patient is scored as "drop out".
	The patient cannot be contacted to make appointments.	The patient is scored as "drop out".
	The patient decides to withdraw his informed consent or study participation.	The patient is scored as "drop out".
Study	One or more patient(s) show severe unwanted side effects to treatment.	Individual counteractive measures are taken. The study is halted.
	More than four patients show unwanted side effects to one treatment or material used.	Individual counteractive measures are taken. The study is halted.

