18.2 Serious Adverse Events

Emergency contact details for reporting of serious adverse events are included in the CIP (Appendix A5).

Serious Adverse Events are adverse events that:

- a) led to a death,
- b) led to a serious deterioration in health that either:
 - 1) resulted in a life-threatening illness or injury, or
 - 2) resulted in a permanent impairment of a body structure or a body function, or
 - 3) required in-patient hospitalization or prolongation of existing hospitalization, or
 - 4) resulted in medical or surgical intervention to prevent life threatening illness or injury or permanent impairment to a body structure or a body function.
- c) led to fetal distress, fetal death or a congenital abnormality or birth defect.

In case of a serious adverse event and subsequent need for un-blinding the name-code list can be assessed immediately and breaking the code will not cause any further problem. The data recorded until the report of adverse event will remain included in the dataset.

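### Section 9.5 provides repair or replacement for an unsatisfactory Icon resin only, which conflicts with the stated blinding and leaves a re-treated lesion without a scoring rule, so the primary comparison could be biased in either direction

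*Combined protocol and SAP*

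**What the plan says.** On recall visits, protocol section 9.5 (Follow-up Evaluations) has every lesion assessed on the same criteria, including surface roughness, colour match, sensitivity and secondary caries. It then adds: "In the event an Icon resin is unsatisfactory, details of the mode of failure will be documented and the necessary replacement / repair made". The placebo site has no corresponding sentence.

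On blinding, section 9.3 (Randomization) states that clinicians and patients "receiving the two treatments will be blinded as to the treatment applied to the specific tooth". Section 11.4.2 (Blinding) states that "the investigators are blinded as to the material used, as are the patient and the evaluators". The one unblinding route described is in section 18.2: "In case of a serious adverse event and subsequent need for un-blinding the name-code list can be assessed immediately".

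On scoring, Table 14.2 (section 14.2) has two lesion-level causes of failure: radiographic progression into the middle or inner third of dentin, and pulpitis. For the first, the consequence is: "The lesion is treated invasively by removing the caries and placing a filling". Both apply to any allocated lesion. The section 11.4.3 visual scale has a code for a restoration but none for a repaired or re-infiltrated lesion. The SAP (Statistical Analysis) defines the primary outcome as the proportion of lesions that needed a filling by 3 years, compared with Fisher's exact test. Change in lesion-depth category is secondary.

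Section 6.4 adds that, if lesion management proves insufficient, "the study will provide a maximum of 2 traditional restorations for free to participants". That provision does not distinguish the two teeth.

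**The concern.** An extra intervention open to one arm only changes what is being compared. The Icon arm becomes infiltration plus repair as needed, while the control arm remains a single placebo application. If the extra intervention prevents or delays a filling and is not counted, the difference in fillings is credited to one Icon application.

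The second issue is blinding. A rule that names one material can be applied only by someone who knows which tooth has it. Each patient has one Icon and one placebo tooth, so this reveals both. Whether a lesion needs a filling is a clinical decision taken at dental examination, and knowledge of allocation can influence it.

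**Working it through.** **Sections side by side**

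1. *Which site the rule covers.* Section 9.5 assesses all lesions but names only the Icon resin for repair. Section 9.4.2 names the placebo material and the Icon resin separately when describing polishing, so it cannot simply be assumed that Icon means either material in 9.5.
2. *Whether it can operate blinded.* Sections 9.3 and 11.4.2 keep clinicians, patients, investigators and evaluators blinded. Section 18.2 opens the code only for a serious adverse event. An unsatisfactory resin has no such route.
3. *How the result is counted.* This depends on what replacement or repair means:
   - Repeat infiltration or repair: not in Table 14.2, no code in 11.4.3, not a filling in the SAP. The lesion is a non-event unless it later progresses, shows pulpitis or is filled.
   - Replacement by a filling: counted by the SAP primary outcome and by the restoration code in 11.4.3.

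The first reading lowers the Icon event count; the second raises it. By contrast, Table 14.2 does address treatment by an external dentist (the patient becomes a drop-out).

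**Size, by illustration only**

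The plan gives no figure on this point. Its evaluable number is 150 × (1 − 0.20) = 120 patients (section 11.2), hence 120 lesions per arm. The re-treatment rate, the share of re-treated lesions that would otherwise have been filled, and the filling rate are all assumptions.

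*Fillings missing from the Icon count.* Re-treated lesions: 0.02 × 120 = 2.4 to 0.10 × 120 = 12. If half would otherwise have been filled: 1.2 to 6.

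*Effect on the planned test.* Suppose both arms truly need fillings at the same rate p, and a share r of Icon failures is kept out of the count. The chance of a false result in favour of Icon is the sum, over control counts i and Icon counts j with j < i and two-sided Fisher P ≤ 0.05, of Bin(i; 120, p) × Bin(j; 120, p(1 − r)). Fillings lost are 120 × p × r.

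| Assumed p | r = 0 | r = 10% (fillings lost) | r = 25% (fillings lost) |
|---|---|---|---|
| 10% | 1.4% | 2.6% (1.2) | 6.3% (3) |
| 20% | 1.7% | 4.1% (2.4) | 13.1% (6) |
| 40% | 1.9% | 7.6% (4.8) | 32.1% (12) |

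The last cell is extreme: 12 lost fillings means that all 12 lesions at the 10% re-treatment rate would otherwise have failed.

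*Opposite direction.* With p = 20% and Icon replacements counted as extra fillings, the Icon rate becomes 20% + a. The same sum with j > i gives a false result against Icon of 4.1% at a = 2 points (2.4 lesions) and 11.8% at a = 5 points (6 lesions).

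These sums treat the arms as independent, as Fisher's test does. Correlation within patients would change the values but not the direction.

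**The case against.** The strongest reply is that this is loose wording. The two materials are described as alike in delivery, colour and viscosity, so Icon resin may stand for whichever study material was applied, and the same recall criteria apply to all lesions. That is possible, but the text does not say so.

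Several further points stand and limit the concern:

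- A reader might infer that the comparison is tilted towards Icon. The documents do not support this. If replacement means a filling, it is counted and works against Icon.
- A reader might infer that a re-treated Icon lesion remains a success unless it is filled. Table 14.2 also scores pulpitis as failure, and radiographic progression is still captured in the secondary outcome.
- A reader might infer that evaluators are bound to be unblinded. Section 11.3 lists four operators and two recall examiners without saying whether they overlap, so the person repairing need not be the person scoring. Section 9.3 also describes the draw box both as A/B and as naming the treatments, which is a separate strain on blinding.
- Section 9.5 already requires the mode of failure to be documented, so part of the recording exists. The CRFs and the text of both amendments are not visible here; the absence of a counting rule means absence from the visible text.
- An unsatisfactory resin need not mean caries progression, since roughness and colour match are among the criteria. The assumed rates have no source.
- At the rates of the SAP's sizing study (32% and 70%), the effect would not overturn the result: 0.32 × 120 ≈ 38 plus 6 gives 44, against 0.70 × 120 = 84, and Fisher P is about 4 × 10⁻⁷. These are progression rates, however, and the primary outcome is fillings, for which the documents give no rate. For the same reason, missing fillings should not be measured against the infiltrated progression rates in section 4.3.4.

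**Conclusion.** The point holds as an unresolved conflict with a possible bias of unknown direction and size. As written, section 9.5 gives one arm an extra intervention, cannot be followed under sections 9.3 and 11.4.2 without identifying both teeth, and produces lesions that no visible rule scores.

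The illustrative range is about 1 to 6 Icon fillings missing out of 120 lesions, resting on an assumed 2-10% re-treatment rate with half otherwise filled. At an assumed 20% filling rate, hiding 2.4 to 6 fillings raises the chance of a false finding for Icon from 1.7% to between 4.1% and 13.1%. Comparable numbers counted as extra fillings would push the other way. If few resins are re-treated the effect is negligible, but under the present plan a reader of the results could not tell. No bias has been demonstrated.

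**What to change.** Reconcile protocol sections 9.3, 9.5, 11.4.2 and 14.2 and the SAP primary outcome on three questions: which sites the repair provision covers, how it operates under blinding, and how a repaired, re-infiltrated or replaced site is scored. Which clinical rule applies is for the investigators; the documents need only agree.

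Extend the failure-mode documentation in section 9.5 to record any repair or repeat application at either site by tooth code, with date, reason and whether allocation was revealed.

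In the SAP, report the number of re-treated lesions by arm. Add a sensitivity analysis of the primary outcome that counts re-treated lesions in either arm as failures, separating re-treatment for surface or colour defects from re-treatment for lesion progression.

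The cost is a small CRF addition, one extra analysis and some wording. The sensitivity result may be less favourable to Icon. If re-treatment stays confined to Icon, the analysis can penalise only that arm and should be described as conservative against Icon; the split by reason keeps cosmetic repairs from being read as caries failures.
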